Official Titled: Assessment of Functionality and Performance of a Novel Tracheostomy Tie

NCT02820181

The Date of Document: 08/1/2016.

Background

Tracheotomy is a common procedure for multiple medical indications. Tracheostomy tubes must be securely fixed to prevent movement or decannulation and tracheostomy ties must be exchanged as needed. However, the process of ties exchange is always risky and complicated. A novel tracheostomy tie has been designed to ensure the safety during exchanging and conveniences of cleaning.

Objective: To evaluate if the novel tracheostomy ties promotes and facilitates the safe care of tracheostomies.

Design and Methods: This is a 2 arms open label randomized phase 2 study. Sixty tracheotomy patients without an existing neck injury will be recruited. Patients in experimental group wear a novel designed tracheostomy tie, the primary feature of which is double belts to ensure the safety during exchanging and conveniences of cleaning. The traditional one was used in control group.

Inclusion criteria include: 1. Subjects ≥ 18 years old and ≤ 60 years old; 2. Patients with a tracheostomy; 3. With intact neck skin; 4. Willingly signs the Informed Consent; 5. Is qualified to participate in the opinion of the Investigator; 6. Without disorders of consciousness. Exclusion criteria include: 1. With an existing neck injury or infection or clinically significant skin diseases on the application site which may contraindicate participation, including psoriasis, eczema, atopic dermatitis, active cancer; 2. With damaged skin or conditions on the application site which includes sunburn, scars, moles or other disfiguration of the test site; 3. Has a known or stated allergy to adhesive bandages, or any of the product types being tested.

4. Uses of topical drugs on the application site; 5. Uses lotions, creams or oils on the application site; 6. Can not communicate with nurses or doctors for any reasons

Outcome measures

Primary Outcome Measure:

1.Subjective index: Difficulty level of exchanging or cleaning the tracheostomy ties. Nurses will be evaluated by Visual Analogue Scale/Score to measure the difficulty level of exchanging or

cleaning the tracheostomy ties.

2.Objective index: local skin breakdown. Scale for surrounding skin breakdown of tracheotomy wound was rated as mild, moderate, or severe. "Mild" wounds included fragile skin that was erythematous or had a small amount of breakdown (<1 cm in diameter). Wounds with evident skin erosion or breakdown associated with drainage and/or pain were classified as "moderate." "Severe" wounds were defined as a partial-thickness loss of dermis presenting as a shallow open ulcer with a red-pink wound bed.

Secondary Outcome Measure:

- 3. Subjective index:degree of comfort during wearing or exchanging tracheostomy ties. Visual Analogue Scale/Score will be used to measure the degree of comfort of patients during wearing or exchanging tracheostomy ties
- 4. Objective index:the actually frequency of exchanging dressing. The record of the frequency of exchanging dressing under the tracheostomy ties in practice will be collected.

Statistical analysis plan:

The hypothesis of this phase II study is that the use of the novel tracheostomy tie will be more comfort and easier to manipulate than traditional one without compromise to safety.

The data will be collected 14 days after tracheostomy. The wound breakdown and the actually frequency of exchanging dressing will be evaluated and recorded by nurse in charge. The visual analogue scale/score of outcome measurements will be administered to the patients and nurses respectively.

Visual Analogue Scale/Score of difficulty level of exchanging or cleaning the tracheostomy ties, degree of comfort during wearing or exchanging tracheostomy ties and the actually frequency of exchanging dressing between the experimental group and control group will be compared using independent sample T-test. Data analysis of the rate of skin breakdown will performed using Fisher's exact test. Statistical analysis will be performed with the SPSS software version 17.0. Significance will be set at P<0.05.

This study is planned to last for 1-2 years.

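### Open label with no step to keep patients unaware of which tie is new: the self-rated comfort score, the only evidence for greater comfort, may carry expectation bias

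*Combined protocol and SAP*

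**What the plan says.** The Design and Methods paragraph gives the only statement on masking: "This is a 2 arms open label randomized phase 2 study". It does not say separately what patients, nurses or assessors know. The arms differ physically: "Patients in experimental group wear a novel designed tracheostomy tie, the primary feature of which is double belts", while for the comparator "The traditional one was used in control group".

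On comfort, Secondary Outcome Measure 3 says: "Visual Analogue Scale/Score will be used to measure the degree of comfort of patients during wearing or exchanging tracheostomy ties". The inclusion criteria require patients to be "Without disorders of consciousness", and those who cannot communicate with staff are excluded, so every rater of comfort is aware and able to respond. Each patient also "Willingly signs the Informed Consent"; the consent text is not part of the public document.

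The statistical analysis plan hypothesises that "the use of the novel tracheostomy tie will be more comfort and easier to manipulate than traditional one without compromise to safety". Comfort is compared between groups by an independent-samples t-test at P<0.05, with data collected 14 days after tracheostomy.

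**The concern.** Comfort is listed as secondary but comes first in the hypothesis. No other outcome measures it: the difficulty VAS is the nurses' own score, and skin breakdown and dressing frequency are recorded by the nurse in charge. If patients know that they wear the new device, they may score comfort differently for that reason alone. The t-test compares two means and cannot separate such a shift from a real gain.

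Nurses handle the ties and cannot reasonably be masked to a double-belt design. Patients are in a different position. Each wears one assigned type, and a patient can feel or see a belt without having been told which design is under test. Some protection is therefore possible for the patient-reported score that is not possible for the nurse-reported one. The plan neither provides it nor says why it was left out.

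**Working it through.** **Plan's own figure.** The plan gives no figure for masking or bias. Its sample size ("Sixty tracheotomy patients without an existing neck injury will be recruited") comes without effect size, SD or power, so it cannot be reproduced. For scale, with 30 per arm and two-sided 5%, the normal approximation gives a difference detectable with 80% power of (1.960 + 0.842) × √(2/30) = 0.72 SD.

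**Inputs from the documents**
- Total of 60 patients (Design and Methods).
- Independent-samples t-test, P<0.05 (Statistical analysis plan).

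**Assumptions, not in the documents**
- Equal allocation, so n = 30 per arm, and a two-sided test.
- No true difference in comfort.
- Knowledge of the tie shifts the mean score by b SD in favour of the novel tie, with b from 0.2 to 0.5. On a 100-mm scale, a 5-mm shift with SD 25 mm is 5/25 = 0.20, and a 10-mm shift with SD 20 mm is 10/20 = 0.50. In between, 5/20 = 0.25 and 10/25 = 0.40.

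**Formula.** Degrees of freedom are 2 × 30 − 2 = 58 and the critical value is 2.002. The noncentrality parameter is b / √(2/30). The chance of a significant result favouring the novel tie is the probability that a noncentral t variable with these parameters exceeds 2.002.

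| Assumed shift b (SD) | Noncentrality | Chance of significance favouring the novel tie |
|---|---|---|
| 0 | 0 | 2.5% |
| 0.10 | 0.387 | 5.7% |
| 0.20 | 0.775 | 11.5% |
| 0.25 | 0.968 | 15.7% |
| 0.40 | 1.549 | 33.1% |
| 0.50 | 1.936 | 47.8% |

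**Two further checks**
- *Sample size is no remedy.* With 60 per arm (118 degrees of freedom), b = 0.20 gives 19.1% instead of 11.5%. A systematic shift becomes easier to detect as the sample grows.
- *Direction.* The table covers only shifts towards the novel tie. A shift of 0.20 SD the other way would leave a 0.3% chance of a result favouring it, and would hide part of any real gain.

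**The case against.** The case against has five parts.

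1. **The bias is not shown.** A reader might infer that the comfort score does contain the patient's knowledge of wearing an improved tie. The documents do not support that. What patients are told would be in the consent material, which is not available, and the Background presents the novel tie as a gain in safety and cleaning, not in comfort. This stands: the bias is a risk, and every rate for a non-zero shift in the table depends on an assumed shift.
2. **Comfort is secondary.** The nurse difficulty score and skin breakdown are untouched. This stands and limits the weight of the point. It does not dispose of it, because the hypothesis still claims greater comfort and has no other evidence for it.
3. **Masking may fail.** Patients enter with a tracheostomy and may already have worn a traditional tie, so a change to double belts could show them which is new. Unmasked nurses may also tell them. This stands: full blinding is doubtful, and the 2.5% rate marks the absence of a shift, not what the fix will achieve.
4. **The remedy is not free.** A reader might infer that patients could be kept unaware at almost no cost. The documents say nothing on feasibility or cost, and neutral consent wording needs ethics agreement.
5. **This is an ordinary limitation.** An open-label design is openly declared for a visibly different device in a small phase 2 study, and nothing in the plan contradicts itself. That is true, but a partial safeguard for the one patient-reported score needs no extra patients or staff, and the plan does not consider it.

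**Conclusion.** The point holds as a risk to one secondary outcome. The trial is open label, no step limits what patients know about which tie is new, and the self-rated comfort VAS is the sole support for the comfort claim. The size and direction of any bias are unknown.

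The range of about 12% to 48% applies only if the shift favours the novel tie, lies between 0.2 and 0.5 SD, and the arms hold 30 patients each. It illustrates how sensitive the test is; it does not estimate this trial's error rate. How much of the excess neutral wording would remove cannot be calculated from the documents. The point is a worthwhile low-cost improvement and does not put the primary comparisons in doubt.

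**What to change.** - Use neutral names, such as Tie A and Tie B, on patient-facing material and on the comfort VAS form, as far as ethics approval allows. Avoid words that mark one design as new or better.
- Have patients mark the comfort VAS without the caring nurse seeing it.
- In Design and Methods, say that nurses are unmasked and that masking of patients is partial, because some may have worn a traditional tie before or may hear their arm from nurses.
- State in the analysis plan that the comfort result will be interpreted with that limitation. If neutral information proves not to be feasible, say so and keep the limitation.

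Two additions that may suggest themselves are better left out. Fitting a new tie in both arms at randomisation could add an exchange, which the Background itself describes as risky, and would not hide a change of design. Reporting comfort by patients' guesses at day 14 would mislead: the guess is made after randomisation and may itself reflect how comfortable the tie was.

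**Cost:** ethics agreement to the neutral wording and a short script for nurses. Sample size, primary outcomes and the test stay as they are. The drawback is that the bias is reduced only in part.

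### The trial claims no loss of safety but plans no record of tube displacement or decannulation, the hazard its own Background names

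*Combined protocol and SAP*

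**What the plan says.** The combined protocol and SAP sets out the safety rationale in four places.

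- **Background:** "Tracheostomy tubes must be securely fixed to prevent movement or decannulation". Of changing the ties it adds: "However, the process of ties exchange is always risky and complicated".
- **Objective:** "To evaluate if the novel tracheostomy ties promotes and facilitates the safe care of tracheostomies".
- **Design and Methods:** the novel tie is described by its double belt, "the primary feature of which is double belts to ensure the safety during exchanging and conveniences of cleaning". Safety during exchange is therefore one of two stated purposes; ease of cleaning is the other.
- **Statistical analysis plan:** the hypothesis is that "the use of the novel tracheostomy tie will be more comfort and easier to manipulate than traditional one without compromise to safety".

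Outcome measures lists four items: nurse VAS for difficulty of exchanging or cleaning the ties (primary), skin breakdown graded in three levels (primary), patient VAS for comfort (secondary), and how often the dressing under the ties is changed (secondary).

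On data collection, the Statistical analysis plan says: "The wound breakdown and the actually frequency of exchanging dressing will be evaluated and recorded by nurse in charge". The VAS scores come from patients and nurses. The planned analyses are t-tests for the two VAS scores and dressing-change frequency, and Fisher's exact test for skin breakdown.

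**The concern.** The plan identifies a hazard, gives a device feature meant to reduce it, and states a hypothesis that safety will not suffer. It then measures nothing that bears on that hazard. A tie can be quick to change, comfortable and gentle on skin and still hold the tube less firmly, so none of the four outcomes can stand in for tube security.

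Two things are at stake. The trial could conclude that safety was preserved even if displacements were more frequent with the novel tie. And if the double belt does make exchange safer, the trial has no means of showing it.

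**Working it through.** **Step 1. Does anything capture the hazard?** The plan states no figure on this point to reproduce, so the check is to go through every outcome, collection step and analysis.

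| Item | What it measures | Collected from | Analysis | Tube security? |
|---|---|---|---|---|
| Primary 1 | Difficulty of exchanging or cleaning ties (VAS) | Nurses | t-test | No, a rating of effort |
| Primary 2 | Skin breakdown, three grades | Nurse in charge | Fisher's exact test | No, skin only |
| Secondary 3 | Comfort (VAS) | Patients | t-test | No |
| Secondary 4 | Dressing-change frequency | Nurse in charge | t-test | No |

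There is no adverse-event or device-incident record either. Skin breakdown is the only harm-type outcome.

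**Step 2. What could 60 patients show if the events were recorded?** Inputs from the document: 60 patients, significance at P<0.05. Assumptions: 30 per arm (no allocation ratio is stated) and two-sided tests (sidedness is not stated). The document gives no event risk and no margin, so the risks below are illustrative.

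*No events in one arm.* The upper limit solves (1 − p)^30 = α.
- One-sided 95%: 1 − 0.05^(1/30) = 0.0950, or 9.5%.
- Two-sided exact 95%: 1 − 0.025^(1/30) = 0.1157, or 11.6%.

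*No events in either arm.* The Wilson upper limit for 0/30 is z²/(n + z²) = 3.8415/33.8415 = 0.1135. The Newcombe 95% interval for the risk difference is then ±√(0.1135² + 0²), that is, −11.4 to +11.4 percentage points.

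*Fisher's exact test against 0/30.* With equal arms and k events in total, all in one arm, P = 2 × C(30,k)/C(60,k).
- k = 5 (16.7% vs 0%): 2 × 142,506/5,461,512 = 0.052.
- k = 6 (20% vs 0%): 2 × 593,775/50,063,860 = 0.024.

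Six events against none are needed. For novel:control splits from 28:32 to 32:28, the number needed lies between 4 and 6.

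*Power.* If the control risk is 0%, the test rejects only when the novel arm has at least 6 events, so power = P(X ≥ 6) with X ~ Bin(30, p).

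| True risk, novel vs control | Power |
|---|---|
| 5% vs 0% | 0.3% |
| 10% vs 0% | 7.3% |
| 20% vs 0% | 57% |

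*Chance of seeing any signal.* The probability of at least one event among 30 is 1 − (1 − p)^30: 79% at a true risk of 5% and 96% at 10%.

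**Reading.** A non-significant comparison would say almost nothing about safety. A log would still be likely to reveal a problem of 5% to 10% frequency, which the present plan would leave out of the trial data.

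**The case against.** The strongest defence is that the analysis section never defines safety. In a small phase 2 study of ease and comfort, skin breakdown may have been meant as the safety measure, and 60 patients cannot settle a rare-event question anyway. On that view it is enough to narrow the wording of the conclusion.

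Part of this stands. The hypothesis claims an advantage only for comfort and handling, the added data would be descriptive, and narrowing the conclusion would remove the unsupported claim. It does not remove the gap: the document itself names tube movement and decannulation as the hazard and justifies the device partly by safety during exchange. Low power is a reason not to infer safety from a P value; it is not a reason to collect nothing.

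Three narrower objections deserve a reply.

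- *The document does not say the nurse records nothing else.* True. The gap is inferred from silence, but no passage provides a route for these events into the data or the analysis.
- *Without a count of tie exchanges, risk per exchange cannot be estimated.* Also true. The count would be a useful addition, but the proportion of patients with at least one event by day 14 is a valid randomised comparison without it.
- *The cost is uncertain.* Fair. The timing statement can be read as one collection at day 14, and the plan does not say who performs tie exchanges.

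**Conclusion.** The concern holds, with high confidence, and should be fixed. The plan provides no information on tube displacement or decannulation, so the tube-security part of its safety claim cannot be assessed. Skin safety and ease of exchange remain assessable.

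That conclusion rests on the text alone. The precision figures rest on an assumed 30 per arm and two-sided tests, and the power figures also on illustrative risks. They show what recording the events could deliver. They are not a standard the trial must meet, because the document states no acceptable risk or margin.

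**What to change.** 1. **Add a descriptive safety outcome.** Through day 14, the nurse in charge logs each accidental decannulation and, separately, each unplanned tube displacement, using a definition and threshold written before enrolment. Each entry notes whether the event happened during or between tie exchanges. Counting tie exchanges as well is optional, and would allow a per-exchange description.
2. **Report it descriptively.** For each arm, give the number of patients with at least one event, with decannulation and lesser displacement kept apart, exact 95% confidence intervals, and the risk difference with its 95% confidence interval.
3. **Limit the conclusion.** Confine any statement that safety was preserved to the outcomes actually measured, and do not draw it from a non-significant P value.

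A separate, smaller clarification: the second primary outcome is headed "Objective index: local skin breakdown", but its grading reads "Scale for surrounding skin breakdown of tracheotomy wound was rated as mild, moderate, or severe". State whether neck skin under the tie is included as well as skin around the stoma, and record the site.

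**Cost.** Small but not nil: a written event definition, a new log entry for nurses who already collect trial data, and a few lines of analysis text. It should need no extra staff, visits or procedures, though this is an assumption because the document does not describe how tie exchanges are documented. The downside is that the trial is open label, so judging lesser movement is open to bias. That is the reason for keeping it apart from decannulation.

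### The safety clause of the hypothesis has no analysis that can support it unless Fisher's test significantly favours the novel tie: skin breakdown has no confidence interval and no rule for a non-significant result

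*Combined protocol and SAP*

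**What the plan says.** The Statistical analysis plan opens with the hypothesis that "the use of the novel tracheostomy tie will be more comfort and easier to manipulate than traditional one without compromise to safety". It therefore joins superiority on comfort and ease of handling with a claim that safety is not made worse.

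Under Outcome measures, local skin breakdown is the second primary outcome: "Scale for surrounding skin breakdown of tracheotomy wound was rated as mild, moderate, or severe". No other listed outcome measures harm; the rest are nurse-rated difficulty, patient comfort and dressing-change frequency. The whole analysis of breakdown is one sentence, beginning "Data analysis of the rate of skin breakdown will performed using" and naming Fisher's exact test, followed by "Significance will be set at P<0.05". The other outcomes are compared by t-test.

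On design, "This is a 2 arms open label randomized phase 2 study" and "Sixty tracheotomy patients without an existing neck injury will be recruited". Breakdown "will be evaluated and recorded by nurse in charge". The documents give no allocation ratio, sidedness, expected breakdown rate, confidence interval, acceptable excess or rule for a non-significant result.

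**The concern.** A test of difference supports a no-worse claim in one case only: when it significantly favours the new device. A non-significant P value shows that a difference was not demonstrated. It does not show that harm above some size has been excluded; for that an interval is needed.

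If the two ties are truly equal on breakdown, the safety clause is true, yet the expected output of the plan is a non-significant P value about which the plan says nothing. The plan does not state that such a result will be read as safe. It leaves the wording open until the results are known, in an open-label trial whose breakdown outcome is rated by the nurse in charge.

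The reach of the outcome is a second limit. Design and Methods describes the tie's double belt as "the primary feature of which is double belts to ensure the safety during exchanging and conveniences of cleaning", but no listed outcome measures harm during exchange. Any safety conclusion can therefore concern skin breakdown only.

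**Working it through.** **Inputs.** From the documents: 60 patients, two arms, Fisher's exact test, significance at P<0.05. Assumed because not stated: 30 per arm, a two-sided test, and the breakdown rates shown as ranges below. The plan has no figure of its own to reproduce, because the 60 comes without an effect size, event rate, power or margin.

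**Step 1: how often the test can support the clause.** Let X be the number with breakdown on the novel tie and Y the number on the traditional tie, with X ~ Bin(30, pN) and Y ~ Bin(30, pT). Summing P(X=x)·P(Y=y) over all 31 × 31 tables with Fisher P<0.05 and x<y gives:

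| True rates (traditional → novel) | Significantly favours novel |
|---|---|
| 10% → 10% | 0.5% |
| 20% → 20% | 1.1% |
| 30% → 30% | 1.3% |
| any equal rate, 1–99% (maximum) | 1.4% |
| 20% → 10% | 9.5% |
| 40% → 20% | 30% |
| 60% → 30% | 56% |

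With 40:20 allocation in either direction, the maximum at equal rates is 2.3%.

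**Step 2: how much harm a non-significant result can hide.** The same enumeration gives the chance of P≥0.05 when the novel tie truly doubles breakdown:

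| True rates (traditional → novel) | Missed, 30 per arm | Missed, 27 per arm (illustrative 10% loss) |
|---|---|---|
| 10% → 20% | 90% | 92% |
| 20% → 40% | 70% | 74% |
| 30% → 60% | 44% | 52% |
| 40% → 80% | 15% | 20% |

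**Step 3: what an interval would show.** The Newcombe 95% interval for the risk difference d (novel minus traditional) combines the Wilson limits (l, u) of each arm:

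- lower = d − √[(pN − lN)² + (uT − pT)²]
- upper = d + √[(uN − pN)² + (pT − lT)²]

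The Wilson limits are 0.0951 to 0.3731 for 6/30 and 0.2459 to 0.5768 for 12/30.

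- Both arms 6/30: d = 0 and √(0.1731² + 0.1049²) = 0.202, so the interval is −20 to +20 points (P=1.00).
- Traditional 6/30, novel 12/30: d = 0.20. Lower = 0.20 − √(0.1541² + 0.1731²) = −0.032; upper = 0.20 + √(0.1768² + 0.1049²) = 0.406. The interval is −3 to +41 points (P=0.16).

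Under the plan both results are simply non-significant, although one shows identical rates and the other an observed doubling.

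**Step 4: the typical case.** With truly equal rates of 10%, 20% and 30%, the median upper limit among non-significant results is 16.9, 20.2 and 22.3 points.

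**The case against.** - **The 1.4% is one tail of the test's own error rate.** Any valid two-sided 5% test behaves much like this when the arms are equal, at any sample size. This is correct. The figure shows no fault in Fisher's test; it shows that a test of difference is the wrong instrument for a no-worse claim.
- **The missed-doubling figures describe low power, and an interval does not change them.** Also correct. They show why a non-significant result here says little; they are not a benefit of the fix. They depend on assumed rates, and since the mild grade includes merely reddened skin, even the plausible range is uncertain.
- **A superiority reading is possible.** The Objective speaks of promoting safe care, and skin breakdown is a primary outcome, so Fisher's test could be meant to show benefit. That reading does not displace the explicit hypothesis sentence. Even if the tie halves breakdown, support comes in only 9.5% to 56% of trials for traditional-tie rates of 20% to 60%.
- **Safety is not defined.** True. Taking skin breakdown as the safety measure is an inference, made because it is the only listed harm outcome.
- **Anyone can compute the interval from the two arm counts.** True if the counts are reported. No data are lost, but the plan would still not say in advance which result earns which wording.
- **This is a 60-patient phase 2 study, and the plan does not say that non-significant means safe.** Both are true, and they are why the remedy is modest and demands no margin.

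**Conclusion.** The concern holds, as something that should be fixed. Its core comes from the text alone: a no-worse clause, one test of difference, no interval and no reading rule. Followed exactly, the plan can support the clause only through a significant result in favour of the novel tie, and then for skin breakdown only.

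The size rests on 30 per arm, a two-sided test and assumed event rates. Under those assumptions, truly equal ties yield that result in at most 1.4% of trials, and a typical non-significant result leaves about 17 to 22 points of excess breakdown unexcluded for true rates of 10% to 30%. Unequal allocation moves the first figure only to 2.3%. The ease and comfort comparisons are not affected.

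**What to change.** Add to the Statistical analysis plan:

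1. Alongside Fisher's test, the skin-breakdown risk difference (novel minus traditional) with a two-sided 95% confidence interval by one named method. Newcombe is used here; Miettinen-Nurminen would also serve.
2. A statement that a non-significant Fisher P value will not be read as evidence of safety, and that the interval governs the safety wording.
3. A descriptive safety conclusion by default, limited to skin breakdown and giving the largest excess not excluded. A conclusion that safety was not compromised should be allowed only if the sponsor has justified and fixed a largest acceptable excess in advance and the upper limit falls below it.
4. Which grades count as breakdown, so that the interval refers to one defined event. This, and any such limit, should be fixed before the first outcome assessment.

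**Cost.** The default needs a few sentences and one interval from two counts, with no more patients. The price is a weaker safety statement.

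The optional limit costs more. The documents give no basis for one, and it would often not be met: with equal true rates of 10% to 30%, an illustrative 10-point limit is met in 14% to 18% of trials and a 20-point limit in 43% to 68%. Even 0/30 against 0/30 leaves an upper limit of 11.4 points.

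The two methods can also disagree near the boundary. Traditional 8/30 against novel 16/30 gives P=0.064 but an interval of +2 to +47 points. Under item 2 this would be reported as an interval wholly on the side of excess breakdown with the novel tie, whatever the P value.

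### Skin breakdown is graded by severity, but the only planned analysis is Fisher's test on a rate, so worse wounds at similar incidence would show as no difference

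*Combined protocol and SAP*

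**What the plan says.** Under Primary Outcome Measure, item 2 is "Objective index: local skin breakdown". Its scale has three ordered grades: "Scale for surrounding skin breakdown of tracheotomy wound was rated as mild, moderate, or severe".

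- The lowest grade, mild, limits any breakdown to under 1 cm across and is described thus: "wounds included fragile skin that was erythematous or had a small amount of breakdown".
- The middle grade, moderate, is set by this clause: "Wounds with evident skin erosion or breakdown associated with drainage and/or pain were classified as".
- For the highest grade, severe, the text reads: "wounds were defined as a partial-thickness loss of dermis presenting as a shallow open ulcer with a red-pink wound bed".

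No grade for intact skin is named, although the inclusion criteria require intact skin at entry.

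The Statistical analysis plan says "The wound breakdown and the actually frequency of exchanging dressing will be evaluated and recorded by nurse in charge". The analysis itself is one sentence, "Data analysis of the rate of skin breakdown will performed using" Fisher's exact test, with significance at P<0.05. No sentence says which grades enter the rate, and none plans a comparison or table by grade. The hypothesis in the same section is that the novel tie will be more comfortable and "easier to manipulate than traditional one without compromise to safety".

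**The concern.** The other listed outcomes are nurse-rated difficulty, patient comfort and dressing-change frequency. Skin breakdown is therefore the only listed outcome that measures harm, and the safety part of the hypothesis has nothing else to rest on.

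An any-grade rate answers how many patients had some skin damage. It does not answer how bad the damage was, which the scale was built to record. If the novel tie left incidence about the same but moved wounds from mild towards severe, the planned test would compare two similar proportions and find no difference. That result could then be read as support for safety.

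Two smaller gaps sit beside this. Mild includes skin that is red but not broken, while the analysed event is called breakdown, so the plan should say whether erythema alone counts. Also, a breakdown under 1 cm with pain or drainage fits both the mild and the moderate wording.

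**Working it through.** **Inputs from the documents:** 60 patients, two randomized arms, three grades plus an implied none, alpha 0.05. The plan states no event rate, effect size, power, margin or allocation ratio, so there is no figure of its own to reproduce.

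**Assumptions:** 1:1 allocation (60/2 = 30 per arm), two-sided tests, and all grade distributions below. They show what can happen, not how likely it is.

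**Step 1. One data set, two summaries.** Assume mild/moderate/severe counts of 12/3/1 (traditional) and 6/9/4 (novel).

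- Any grade: 12+3+1 = 16/30 vs 6+9+4 = 19/30. Fisher p = 0.60; risk difference 19/30 − 16/30 = 10 points (95% CI −14 to 33).
- Moderate or worse: 3+1 = 4/30 vs 9+4 = 13/30. Fisher p = 0.020; risk difference 13/30 − 4/30 = 30 points (95% CI 7 to 49).
- Mann-Whitney on none/mild/moderate/severe: p = 0.08.

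The intervals are Newcombe's. Each arm has a Wilson interval, (p + z²/2n ± z√[p(1−p)/n + z²/4n²]) / (1 + z²/n). For moderate or worse these are 0.053 to 0.297 around 0.133, and 0.274 to 0.608 around 0.433.

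- Lower limit: 0.300 − √[(0.433−0.274)² + (0.297−0.133)²] = 0.07.
- Upper limit: 0.300 + √[(0.608−0.433)² + (0.133−0.053)²] = 0.49.

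With equal incidence the contrast is starker. For 14/3/1 vs 6/8/4, any grade is 18 vs 18 (p = 1.00), moderate or worse is 4 vs 12 (p = 0.039), and Mann-Whitney gives p = 0.25.

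**Step 2. Power when every grade worsens.** Multiply the odds of being at or above each grade by 3. For a control distribution of 60/20/12/8% (none/mild/moderate/severe):

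- any grade: 0.40/0.60 × 3 = 2.00, giving 67%
- moderate or worse: 0.20/0.80 × 3 = 0.75, giving 43%
- severe: 0.08/0.92 × 3 = 0.26, giving 21%

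The ranges below cover this control and three others (50/25/15/10, 30/40/20/10 and 70/15/10/5%), with 20,000 simulated trials each.

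| Scenario | Fisher, any grade | Fisher, moderate or worse | Mann-Whitney |
|---|---|---|---|
| Odds ratio 3, worsening | 26-45% | 32-45% | 57-64% |
| Odds ratio 3, improvement | 27-44% | 8-27% | 39-61% |

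With no difference, Fisher's any-grade test rejects in 2.4-2.8% of trials and Mann-Whitney in 4.5-5.1%. Part of the gain is therefore that Fisher's test is conservative at this size.

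**Step 3. Power when only severity shifts.** Total incidence is equal in both arms.

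| Mild/moderate/severe %, traditional vs novel | Fisher, any grade | Mann-Whitney | Fisher, moderate or worse |
|---|---|---|---|
| 45/10/5 vs 15/20/25 | 2.3-2.5% | 29% | 65% |
| 30/15/5 vs 15/15/20 | 2.3-2.5% | 11% | 18% |
| 30/7/3 vs 10/13/17 | 2.3-2.5% | 10% | 37% |
| 50/15/5 vs 20/25/25 | 2.3-2.5% | 38% | 60% |
| 30/7/3 vs 20/13/7; 25/10/5 vs 15/15/10 | 2.5-2.7% | 6% | 9-10% |

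The any-grade test cannot see these shifts. Mann-Whitney sees some of them, less well than the moderate-or-worse cut. In the last row no test is adequate, so intervals are needed.

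**Step 4. What a non-significant result excludes.** With 6/30 in both arms the risk difference is 0, with a 95% CI of −20 to +20 points.

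**The case against.** The best case for the plan is that nothing is really undefined. Patients start with intact skin, the scale puts erythematous skin in mild, and so the rate means any grade against none. Fisher's test is valid for that event. Under a common odds shift the any-grade cut is also a defensible main analysis: for improvement at odds ratio 3 it has more power than moderate-or-worse under all four assumed controls (27-44% vs 8-27%). This stands, and it is why Fisher's any-grade test should be kept.

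Four stronger readings are tempting, and the documents do not support them.

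- *The event has no threshold, so the test cannot be run.* The plain reading largely settles it. What remains open is whether erythema alone counts.
- *The severity data will be thrown away.* The plan makes the grades part of a primary outcome and has the nurse in charge evaluate the wounds. Its silence shows that no use of severity is planned, not that none will be reported.
- *The choice of cut decides the result.* The any-grade and moderate-or-worse tests disagree on significance in 28-36% of simulated trials at odds ratio 3 (worsening), 16-20% at odds ratio 2 and 3-5% with no difference. These rates mainly reflect low power and run both ways: at odds ratio 3, only moderate-or-worse is significant in 8-27% and only any-grade in 9-20%. Picking the best of three cuts afterwards gives 4-6% false positives at 1:1, a minor concern.
- *Skin breakdown is the designated safety endpoint.* The documents never call it that. The link is that no other harm outcome is listed.

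The hidden-harm examples are also constructed, and the ±20-point interval reflects sample size and the missing margin, not the grading. Both objections are fair. The examples show only that the stated analysis cannot detect that pattern.

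**Conclusion.** The point holds as a mismatch between how a primary outcome is measured and how it is analysed. Severity is graded, the hypothesis makes a safety claim, and the single planned test ignores severity on its plain reading. The grades would add information at almost no cost: about 57-64% power for Mann-Whitney against 26-45% for Fisher's any-grade test at a common odds ratio of 3 (worsening). Where only severity shifts, Fisher's any-grade test stays at 2-3%. These figures rest on an assumed 30 per arm and assumed grade distributions, and are illustrative only.

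The change should be made. The omission does not invalidate Fisher's test or the trial.

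**What to change.** 1. Keep Fisher's exact test on any grade against an explicit none level as the main test. State before data are seen whether erythema alone counts.
2. Prespecify one supporting ordinal comparison of none/mild/moderate/severe by Mann-Whitney.
3. Report counts by grade and arm, with risk differences and 95% CIs for any breakdown and for moderate-or-worse breakdown. Base the safety statement on the excess that these intervals do not exclude, not on a non-significant p-value.
4. State in advance that Fisher's any-grade test remains the formal test if the analyses differ, and that the severity results appear beside it in any safety statement.
5. The sponsor should reconcile the mild and moderate wording so that each wound falls in one grade. The moderate-or-worse interval depends on this.

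The cost is a few SAP sentences, a short scoring clarification for the nurse in charge, and one extra supporting test. No patients or measurements are added.
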